4.1 Primary Outcome

Implementation in Terms of Participation. Participation will be determined by the ratio of participants who are successfully enrolled to the total number of eligible patients.

Implementation in Terms of Usage. Usage will be determined by the number of consented participants enrolled in the study who used VOICES to completion.

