Demand	To what extent is VOICES likely to be used?	Size of target population of EM victims in the ED measured by % who screen positive for EM and % who receive the BNI portion of VOICES
Implementation	To what extent can VOICES be delivered to participants in the defined, but not fully controlled, context of the ED?	Degree of execution measured by % of potential participants approached who consent to participate in the pilot study Success of execution measured by # of participants who used the tool to completion and reasons for not completing the tool as reported on post-survey
Practicality	To what extent can VOICES be carried out with intended participants without outside intervention?	Efficiency of implementation measured by the average time (1) to consent & orient participants to the tool and (2) needed to complete VOICES documented by the RA; and (3) patients perceived time of VOICES as measured on post-survey Factors affecting implementation measured by the number and source of interruptions during participation documented by the RA; The number of participants who want their caregiver/family member present during study as documented by the RA Positive/Negative effects of VOICES measured by participants' perceptions of safety concerns vs. benefits as reported on post-survey
Limited Efficacy	Does VOICES show promise of being successful?	Observed trends in proportions of reported (1) portion of participants who change their self-identification response after completing the education (2) portion of participants who change readiness to disclose after completing the BNI (3) exploration of whether self-identification impacts likelihood of self-disclosure Effect-size estimation measured by change in the % of patients who disclose Potential sources of bias measured by (1) sample representativeness & (2) observed group differences of participants measured by demographic data determine through t-tests and chi-square analyses

Table 1: Planned Data Analyses and Interpretation

Data Management. Study data will be entered into the VOICES by the patients through direct use and by the RA through data entry. We will use VOICES Back-end for the study management needs.

SPECIFIC AIM 3: Exploratory Aim: To perform a preliminary evaluation of the accuracy of VOICES as a screening tool in correctly classifying EM cases that were referred to Adult Protective Services (APS).

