- **Exclusion Criteria:** Exclusion criteria are as follows: (1) subjects who live in nursing homes or other long- term care setting and do not reside in community setting; (2) at the discretion of the clinician, patient will be excluded if they cannot safely undergo the studies required for participation; (3) subjects with clear signs of EM; (4) Patient refusal to participate; (5) severe hearing and vision impairment; (6) presenting with active psychotic symptoms; (7) presenting with acute intoxication.

9. How will **eligibility be determined, and by whom?**

VOICES-C Sub Study:

The eligibility be determined by the PI and If the patient meets the initial screening eligibility, and none of the exclusion criteria as described above for VOICES-C.

VOICES-D Sub Study:

The eligibility be determined by the MSU PI and If the patient meets the initial screening eligibility, and none of the exclusion criteria as described above for VOICES-C.

VOICES-Feasibility Study:

Eligibility and Capacity Evaluation: We will use standardized criteria as described below to determine if the potential participant is capable of providing consent. The RAs will be highly trained in obtaining informed consent. They will receive training by the Yale Program on Aging for determining capacity to consent in aging populations. Evaluating the capacity of the participants to understand the purpose, risks, benefits, confidentiality, and privacy associated with study is vital for valid informed consent. The RAs will determine if the subject can participate based on their degree of alertness and if they are oriented to person, place and time and if they are able to communicate in English.

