If the patient meets the initial screening eligibility, and none of the exclusion criteria as described above, the RA will approach the patient and check if they are well enough to participate in the study. The RA will then check if the patient is alert and oriented to person, place, and time. Then, the RA will use Abbreviated Mental Test 4 (AMT-4) to assess cognitive status. If the patient scores < 4 on the AMT-4 then s/he will not be eligible to be enrolled in the study. If the patient scores 4 on the AMT-4, then the RA will introduce the study and ask if s/he is interested in participating in the study. Factors to be considered include the ability to articulate a choice regarding study participation, understand its purpose, and comprehend that participation does not constitute medical treatment. If the patient is deemed capable and chooses to participate in the study, then the RA will perform the informed consent process to find out if the individual is still interested in participating in the study. The timing of the informed consent will take place as described below:

1. The RA goes to the older adult's room, if the caregiver is there, S/he will be asked to wait in the ED waiting room.
2. Escort the caregiver (if any) to wait in the waiting area
3. Introduce the study to the older adult when s/he is alone
4. If the older adult agrees to participate, conduct the bedside screening that includes these questions: Is the patient well enough to participate? Is the patient able to hear the instructions from the iPad through the headphone provided? Is the patient able to see instructions and demonstrations on the iPad screen? Is the patient alert and oriented to person, place, and time? Does the patient have a AMT-4 score of 4?)
5. If all of the above was completed and the older adult is eligible and agrees to participate, start the informed consent process that will include all the eight basic elements of informed consent mentioned above and the additional elements of informed consent.

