7. ANALYTIC PLAN
 - 7.1. Analysis of Primary Outcome
 - 7.2. Analysis of Other Pre-Specified Outcome Measures

REFERENCES

STUDY SUMMARY (revised 3/1/2023)

Title	Virtual cOaching in making Informed Choices on Elder Mistreatment Self-Disclosure (VOICES)
Study Design	The design is a single arm trial to develop the digital intervention and conduct a feasibility study across five important areas including: acceptability, demand, implementation, practicality, and limited efficacy.
Study Duration	16 months
Trial Sites	Yale-New Haven Hospital Emergency Department on the Saint Raphael's Campus (YNHH-ED-SRC).
Objective	The purpose of this study is to evaluate the feasibility of using VOICES Elder Mistreatment (EM) intervention in the emergency department to detect cases of EM.
Number of Subjects	Over the course of this project, we recruited 1002 participants.
Main Inclusion Criteria	Inclusion Criteria: (1) Age 60 years or older; (2) non-full trauma track upon arrival; (3) Alert and oriented to person, place and time; (4) AMT4=4; (5) Able to consent and communicate in English; and (6) Agrees and able to use the iPad; (7) Not in police custody
Intervention	Our intervention is innovative because it utilizes best practices, and innovations in the design and development of digital health to create the one of its kind VOICES EM Intervention. As an easy-to-use, user-friendly EA intervention that runs on tablets with the information and messages displayed on the screen and spoken through headphones for privacy. VOICES delivers content specifically designed to target three factors (attitudes, subjective norms, perception of control) while providing accurate education on EM and APS response and dispelling myths and stereotypes surrounding victimization. VOICES will address perceptions of control making it easy to self-report and ask for help. Another innovative feature of VOICES is the ability to deliver health information through the use of digital tools, multimedia, and digitally guided interviews to older adults to increase awareness of EM.
Duration of Intervention	One session 8.8 minutes on average
Primary Outcome	The primary outcomes are participation and usage. Participation will be determined by the number of patients enrolled in VOICES. Usage will be determined by the number of patients enrolled in the study that complete the VOICES tool.
Primary Analysis	Primary outcomes will be tabulated as counts and frequencies.

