3. STUDY DESIGN

The design is a single arm trial to develop the digital intervention and conduct a feasibility study across five important areas including: acceptability, demand, implementation, practicality, and limited efficacy. The primary outcomes are participation and usage. Participation will be determined by the number of patients enrolled in VOICES. Usage will be determined by the number of patients enrolled in the study that complete the VOICES tool. Over the course of this project, we recruited 1,002 subjects over 16 months.

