7 ANALYTIC PLAN

7.1 Analysis of Primary Outcome:

Implementation in Terms of Participation. Participation will be determined by the ratio of participants who are successfully enrolled to the total number of eligible patients. The numerator, denominator, frequencies and 95% confidence intervals will be reported.

Implementation in Terms of Usage. Usage will be determined by the number of consented participants enrolled in the study who used VOICES to completion. The numerator, denominator, frequencies and 95% confidence intervals will be reported.

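### The SAP defines the primary outcome Participation as a count in two places and as enrolled/eligible in three, and does not say whether patients who refuse are eligible

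*SAP*

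**What the plan says.** **SAP, count.** The Study Summary (Primary Outcome row) and section 3 both say "Participation will be determined by the number of patients enrolled in VOICES". The Primary Analysis row of the Study Summary adds "Primary outcomes will be tabulated as counts and frequencies".

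**SAP, ratio.** Table 1, section 4.1 and section 7.1 give enrolled over eligible; in 4.1 the words are "Participation will be determined by the ratio of participants who are successfully enrolled to the total number of eligible patients". Section 7.1 continues: "The numerator, denominator, frequencies and 95% confidence intervals will be reported".

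**Protocol, a third measure.** Protocol Table 1 measures degree of execution, in the same Implementation domain, as the percentage "of potential participants approached who consent to participate in the pilot study". It is not labelled primary.

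**Criteria that involve willingness.** Protocol section 8 lists, among the exclusions for the feasibility study, "4) Patient refusal to participate". The inclusion list, repeated in the SAP Study Summary, contains "6) Agrees and able to use the iPad; (7) Not in police custody".

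**Passages that keep eligibility and willingness apart.** Protocol section 9 says "If the patient meets the initial screening eligibility, and none of the exclusion criteria as described above, the RA will approach the patient", and step 5 of its numbered list names being eligible and agreeing as two conditions. The consent-waiver item (Section III, item 9) has eligibility settled by a few bedside questions. The eligibility variables in Section IV, item 1 include no agreement item.

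**The concern.** Participation is one of only two primary outcomes in a study whose purpose is feasibility. A count of enrolled patients shows how much recruitment was done, not how acceptable the tool was to those offered it. Only a proportion does that, and its meaning depends on who is in the denominator.

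The one written rule on refusal, applied to the SAP's ratio, removes the people whose decision the ratio is meant to measure. A reader given a numerator and a denominator could not tell whether refusers were counted. The protocol expects a later comparative effectiveness study, for which uptake is a natural planning input, so the ambiguity would carry forward.

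**Working it through.** Neither document states a participation rate, an eligible count or a target, so there is no planned figure to reproduce. The check compares the texts and then shows what each reading implies.

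**Step 1: the five SAP statements.**

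| Place in SAP | Definition | Denominator |
|---|---|---|
| Study Summary | number enrolled | none |
| Section 3 | number enrolled | none |
| Table 1 | enrolled / eligible | eligible |
| Section 4.1 | enrolled / eligible | eligible |
| Section 7.1 | enrolled / eligible, with 95% CI | eligible |

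All five are current text, not a log of changes. A bare count cannot supply the denominator and interval that section 7.1 requires.

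**Step 2: what each reading gives.** The only input from the documents is the number enrolled, E = 1,002 (SAP Study Summary and section 3). Let R be the number of refusers who meet every other criterion; R is not given.

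- Count: 1,002, with no proportion and no binomial interval.
- Refusers ineligible (criteria read literally): about 1,002/1,002 = 100%, apart from any patient eligible and willing but not enrolled for another reason. The exact lower 95% limit is 0.025^(1/1,002) = 0.996, so the interval is 99.6% to 100%.
- Refusers eligible: 1,002/(1,002 + R).

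The third line can be shown only on assumed values of R. These are illustrations, with Wilson 95% intervals:

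| Assumed R | Ratio | 95% CI |
|---|---|---|
| 111 | 1,002/1,113 = 90.0% | 88.1% to 91.7% |
| 1,002 | 1,002/2,004 = 50.0% | 47.8% to 52.2% |
| 2,338 | 1,002/3,340 = 30.0% | 28.5% to 31.6% |

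The table shows that the second reading does not respond to R and the third does. It does not estimate the true figure.

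**Step 3: can the denominator be counted?** Three points bear on this and are secondary to the refusal rule.

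- *Order of screening.* In protocol section 9 the narrative gives the AMT-4 before the study is introduced. The numbered list introduces the study at step 3 and does the bedside screen, AMT-4 included, at step 4 only if the patient agrees. Under the list, refusers have unknown bedside eligibility.
- *Patients never approached.* Section III, item 3 has research staff on rotating shifts, and item 5 says they cannot approach every ED patient. The SAP's total of eligible patients does not say whether eligible patients whom nobody approached are included.
- *Caregiver to stay.* Protocol section 11 excludes these patients before any study information is given, but section 8 does not list this as an exclusion.

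**Step 4: direction of the unknowns.** Write the refusers as K (known eligible) plus U (bedside status unknown), of whom U* ≤ U would have passed. Then E/(E + K + U) ≤ E/(E + K + U*), so keeping all of U can only understate the ratio among approached patients. If N eligible patients were never approached, E/(E + K + U* + N) is smaller than E/(E + K + U*). Keeping U is therefore conservative about bedside status among approached patients, and is not a lower bound for all eligible patients.

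**The case against.** The strongest reply is that the count wording is synopsis shorthand. The three places that specify the outcome and its analysis agree on the ratio, and an analyst following section 7.1 has one instruction. That is largely right: on count versus ratio, the repair is editorial alignment. It does not settle who is eligible.

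The second reply is that the 100% reading is unintended. Exclusions are checked before the approach, when refusal cannot yet be known. Section 9 step 5, the consent-waiver item and the list of eligibility variables all keep willingness apart, and a ratio of 1,002 to 1,002 would be obvious once the denominator was printed. This stands as evidence of intent. A reader might infer that the trial will report, or has reported, an inflated participation rate; the documents do not support that. What remains is that the only explicit rule on refusal points the other way, and printing a denominator does not say who is in it.

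The third reply is that no hypothesis, threshold or decision depends on the figure. This stands and limits the weight of the point.

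A reader might also want to put a size on the effect, for instance by using the protocol's 20% planning allowance for cognitive ability (section 13) as a bedside failure rate among refusers. That figure adjusts expected prevalence; it is not a screening failure rate, and the bedside screen also covers wellness, hearing and vision.

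**Conclusion.** The point holds and should be fixed. The two-against-three split in the SAP is certain from the text. So is the absence of a rule on refusal in the SAP, alongside protocol criteria that would remove refusers if applied literally. The probable intent is that refusers count as eligible, but a primary outcome should not depend on the reader inferring it.

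The size cannot be determined from the documents. The only fixed values are the count of 1,002 and the literal ratio of about 100%; anything below that rests on an assumed number of refusers. Because the study is single-arm and descriptive with no success criterion, the consequence is an uptake figure that cannot be interpreted or carried into planning with confidence. It is not a wrong formal decision.

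**What to change.** 1. Change the Study Summary and section 3 of the SAP to the ratio used in Table 1, 4.1 and 7.1, with its 95% confidence interval.
2. Define Participation as enrolled divided by approached patients who meet all criteria other than willingness, disregarding exclusion 4 and the agreement part of inclusion 6.
3. State that eligible patients never approached are outside the denominator, and report their number if it was recorded.
4. Keep refusers with unknown bedside status in the denominator and report their number where recorded. Describe the ratio as conservative only with respect to that unknown status among approached patients.
5. State where patients who wanted a caregiver to stay are counted.
6. Reconcile the two screening sequences in protocol section 9 by stating which was used.

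The cost is a few sentences of SAP wording and a count of patients from the study enrollment records, which Table 1 of the SAP names as the source. The reported figure may be less favourable. Recruitment is already described as complete at 1,002, so some counts may not be available. Protocol Table 1 has staff document participants who want a caregiver present, but section 11 excludes such patients beforehand, so this does not show that they were logged. Where a count is missing, the report should say so.

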4.2 Other Pre-Specified Outcomes

Acceptability: Participant satisfaction will be measured along multiple dimensions using post-use satisfaction survey with two 5-point Likert response set scales, developed by the research team. Scale 1: Likert scale 1-5, where 1= Very Dissatisfied, and 5= Very Satisfied Scale 2: Likert scale 1-5, where 1= Strongly Disagree, and 5= Strongly Agree

Demand: Demand will be assessed through examining how likely will VOICES be used by patients. To do this, the size of target population of EM victims in the ED will be

measured by the % of the patients who self-identified with elder mistreatment and the % who receive the Brief Negotiation Interview (BNI) portion of VOICES.

Practicality: Practicality will be assessed by observing the ease of VOICES use by patients. To do this, a series of steps will be watched to determine the efficiency of implementation measured by the average time (1) to consent & orient participants to the tool and (2) needed to complete VOICES documented by the Research Assistant; and (3) patients perceived time of VOICES as measured on post-survey. Each of these will be reported as part of the overall outcome.

Efficacy of the Educational Material: To understand the efficacy of VOICES in this pilot, we will look at how many participants changed their self-identification response after completing the educational component.

Efficacy of the Brief Negotiation Interview: We will look at how many patients changed their readiness to identify and readiness to disclose after completing the Brief Negotiation Interview (BNI).

Efficacy of Self-Identification on Self-Disclosure: We will explore whether self-identification impacts likelihood of self-disclosure. Effect-size estimation measured by change in the % of patients who disclose among those who self-identified.

Accuracy: To understand the accuracy of the VOICES tool, a preliminary evaluation of the accuracy of VOICES as a screening tool in correctly classifying EM cases that were positive based on social worker assessment, and those referred to Adult Protective Services (APS). The percent correct classification will be reported.

5. RANDOMIZATION

Randomization is not applicable with the single arm design.

6. SAMPLE SIZE

6.1 Sample Size Determination for the Primary Outcome

Given that VOICES is a new tool, we did not have the needed information to estimate a power analysis or judge an approach sample size to calculate a meaningful sensitivity analysis when planning for the study. However, based on the initial analysis of the relevant population and our sample size, we estimate VOICES will detect EM in 40 to 70 older adults. We will report the 95% confidence intervals with our finding of sensitivity.

